The cartridge that houses the VTL C3A cells contains approximately eight thousand hollow fibers made up of a semi-permeable polysulfone material that has a nominal pore size of 0.2- μ m ([Brotherton 2007](#)). During ELAD treatment, an extracorporeal pumping system pumps the subject's ultrafiltrate through the hollow fibers of the cartridge wherein the semipermeable membrane permits a bidirectional flow between the cells (grown between the hollow fibers) and the ultrafiltrate (contained in the lumen of the hollow fibers). Toxins, nutrients and dissolved oxygen pass from the ultrafiltrate to the cells, while the potentially-beneficial macromolecules and other substances synthesized by the cells simultaneously pass into the patient's ultrafiltrate.

After circulation through the cartridges, the ultrafiltrate passes through a 0.2- μ m pore size filter, is recombined with the cellular components of the subject's blood, and is returned to the patient through the dual-lumen catheter. The toxins metabolized by the VTL C3A cells are thereby returned to the subject to be excreted by the renal or gastrointestinal system. This circulation is maintained continuously for the duration of ELAD treatment, typically between three and five days.

Adverse Events: ELAD System (Device)

Adverse events should be attributed to the ELAD System when malfunctions of the bedside unit or contamination of catheters, tubing sets or filter components arise while the subject is undergoing ELAD treatment.

Expected Adverse Events: ELAD System¹ (Device)

Based on a review of safety data from past clinical studies and investigator assessments of AEs in the VTI-208 study, the following AEs could potentially be related to the ELAD System:

Abdominal infection	Coagulopathy	Hypocalcaemia	Pyrexia
Activated partial thromboplastin time prolonged	Catheter site haemorrhage	Hypofibrinogenaemia	Rectal haemorrhage
Air embolism	Disseminated intravascular coagulation	Hypotension	Thrombocytopenia
Allergic reaction	Haemorrhage	Hypothermia	
Anemia	Hemolytic anaemia	Infection	
Anaphylactic reaction	Hypersensitivity	Lung Infection	

¹ Listed alphabetically

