Abdominal distension	Device related sepsis	Hypernatraemia	Multi-organ failure
Acute respiratory distress syndrome	Disseminated intravascular coagulation	Hypersensitivity	Oedema peripheral
Agitation	Ecchymosis	Hypertension	Oliguria
Allergic reaction	Edema	Hypocalcemia	Pain
Anaemia	Edema peripheral	Hypocoagulable state	Pneumonia
Anuria	Electrolyte imbalance	Hypofibrinogemaemia	Pulmonary oedema
Application site bleeding	Encephalopathy	Hypokalaemia	Renal failure acute
Ascites	Epistaxis	Hypomagnesaemia	Respiratory arrest
Asthma	Fever	Hypophosphataemia	Tachycardia
Atrial fibrillation	Fluid overload	Hypotension	Thrombocytopenia
Bacteremia	Gastrointestinal haemorrhage	Hyothermia	Vessel puncture site haematoma
Blood lactate dehydrogenase (LDH) increased	Gingival bleeding	Hypovolemia	Wound secretion
Blood pressure decreased	Haematemesis	Ileus	
Catheter site hematoma	Haematuria	Infection	
Catheter site hemorrhage	Hemoglobin decreased	Injection site haemorrhage	
Catheter site pain	Hemolysis	Ischemic hepatitis	
Catheter site reaction	Haemorrhage	Leukocytosis	
Coagulation disorder	Hepatic encephalopathy	Melaena	
Coagulation prolonged	Hepatic failure	Mental status changes	

¹ Listed alphabetically

Expected Adverse Events: Extracorporeal Procedures

Certain adverse events are typically observed in patients undergoing treatment with extracorporeal procedures. Anemia, coagulopathy, and thrombocytopenia tend to be the most common adverse events observed during treatment with extracorporeal procedures. Specific details about each of these adverse events are presented in the following sections.

Anemia

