In general, laboratory changes in these critically-ill subjects should not be recorded as AEs. However in certain cases abnormal laboratory changes should be reported as AEs. The suggested laboratory values for hematology, serum chemistry, and urinalysis parameters that occur while the subject is on ELAD treatment that should be reported as AEs are listed in the Investigator's Brochure.

If the subject develops a laboratory abnormality meeting these criteria, a clinical diagnosis should be provided with the reported laboratory abnormality, if applicable. For example, if the subject developed hematuria in the presence of >1.0 g/dL of hemoglobin, hematuria should be listed as the clinical event and include in the details of the AE that a decrease in hemoglobin was associated with the hematuria.

If the laboratory abnormality was not associated with a clinical event, the laboratory abnormality should be listed as an AE and indicate that no clinical findings were present. For example, hyponatremia is not usually associated with any specific clinical diagnosis but is found in

subjects with clinically significant decompensated liver disease, so the specific diagnosis would not be included.

The specific notable laboratory changes for hematology, serum chemistry, and the urinalysis while on ELAD to be reported as AEs are as follows:

Hematology

- Hemoglobin >1.0 g/dL decrease from Baseline in the absence of gastrointestinal bleeding or other clinically overt sources of bleeding (e.g., hematuria, central line bleeding) or hemoglobin levels <7.0 g/dL
- WBC counts <1.5 × 10³/mL in the absence of sepsis or an uncontrolled infection
- Platelet counts <20,000 × 10³/mL and note if there is evidence of impaired clotting or clinical bleeding or oozing

Serum Chemistry

- Abrupt (within 48 hours) reduction in kidney function defined as an absolute increase in serum creatinine of 0.3 mg/dL [≥ 26.4 $\mu\text{mol/L}$ or increase of serum creatinine of 50% or more (1.5-fold) from baseline]
- Hyperglycemia (serum glucose >350 mg/dL)
- Hyperkalemia (serum potassium >7.0 mEq/L)
- Hypocalcemia (serum calcium <3.5 mmol/L)
- Hypoglycemia (serum glucose <50 mg/dL)
- Hypokalemia (serum potassium <2.0 mEq/L)
- Hypomagnesemia (serum magnesium <1.0 mEq/L)
- Hyponatremia (serum sodium <120 mEq/L)
- Hypophosphatemia (serum phosphate <0.3 mmol/L)
- Lactate >4 mmol/L

Urinalysis

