All TEAEs and TESAEs of bleeding that emerged following randomization up to Study Day 91 for each subject will be identified by the terms listed in [Appendix D](#).

Two series of separate tables will be generated for the periods between Randomization and Study Day 7, between Study Day 8 and Study Day 14, between Study Day 15 and Study Day 28 and between Study Day 29 and Study Day 91. The first series will summarize the total number of TEAEs of bleeding emerging post-randomization by Preferred Term and treatment group, and the number of subjects with at least one bleeding TEAE, with more than one bleeding TEAE, along with the number of subjects administered heparin for ELAD treatment or for DVT prophylaxis. The second series will summarize the total number of TESAEs of bleeding emerging post-randomization by Preferred Term and treatment group, and the number of subjects with at least one bleeding TESAЕ, with more than one bleeding TESAЕ, along with the number of subjects administered heparin for ELAD treatment or for DVT prophylaxis.

In addition the number of subjects reporting at least one TEAE and also the number of subjects reporting at least one TESAЕ will be summarized by Preferred Term and treatment group.

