Appendix D Bleeding Search Terms

Aggravated bleeding tendency
Bleeding tendency
Haemorrhagic diathesis
Hemorrhagic diathesis
Haemorrhage abnormal
Haemorrhagic disorder
Haemorrhagic disorder due to circulating anticoagulants
Hemorrhage abnormal
Hemorrhagic disorder due to circulating anticoagulants
Spontaneous haematoma
Spontaneous hematoma
Spontaneous haemorrhage
Spontaneous hemorrhage
Gastric haemorrhage
Gastric varices haemorrhage
Gastroduodenal haemorrhage
Mallory-Weiss syndrome
Oesophageal haemorrhage
Oesophageal varices haemorrhage
Portal hypertensive gastropathy
Anal haemorrhage
Colonic haematoma
Intestinal haematoma
Large intestinal haemorrhage
Mesenteric haematoma
Mesenteric haemorrhage
Portal hypertensive enteropathy
Rectal haemorrhage
Small intestinal haemorrhage
Chronic gastrointestinal bleeding
Gastrointestinal haemorrhage
Haematemesis
Haematochezia
Intra-abdominal haematoma
Intra-abdominal haemorrhage
Lower gastrointestinal haemorrhage
Melaena
Upper gastrointestinal haemorrhage
Application site haematoma
Application site haemorrhage
Catheter site haematoma
Catheter site haemorrhage
Infusion site haematoma
Infusion site haemorrhage
Injection site haematoma

Injection site haemorrhage
Abnormal withdrawal bleeding
Anovulatory cycle
Bleeding anovulatory
Delayed menarche
Dysfunctional uterine bleeding
Dysmenorrhoea
Early menarche
Menometrorrhagia
Menorrhagia
Menstrual discomfort
Menstrual disorder
Menstruation irregular
Metrorrhagia
Polymenorrhagia
Polymenorrhoea
Premenstrual cramps
Premenstrual dysphoric disorder
Premenstrual headache
Premenstrual pain
Premenstrual syndrome
Retrograde menstruation
Withdrawal bleed
Scrotal haematoma
Testicular haemorrhage
Deep dissecting haematoma
Haemorrhage subcutaneous
Haemorrhage subepidermal
Mucocutaneous haemorrhage
Skin haemorrhage
Subcutaneous haematoma
Arterial haemorrhage
Arterial perforation
Bloody discharge
Exsanguination
Extravasation blood
Haematoma
Haemorrhage
Internal haemorrhage
Shock haemorrhagic
Venous haemorrhage

Signature Page for VV-CLIN-002328 v2.0

| | |
|---------|--|
| Approve | [name] Clinical Operations 24-Aug-2018 21:20:02 GMT+0000 |
|---------|--|

| | |
|---------|--|
| Approve | [name] Executive 25-Aug-2018 07:20:20 GMT+0000 |
|---------|--|

| | |
|---------|--|
| Approve | [name] Medical 26-Aug-2018 02:27:43 GMT+0000 |
|---------|--|

Signature Page for VV-CLIN-002328 v2.0

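### SAP Appendix D, the only stated identifier of bleeding events, omits haematuria and epistaxis and includes terms that are not bleeding, so the descriptive bleeding counts can be misstated

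*SAP*

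**What the plan says.** SAP 8.3.1.3 defines bleeding of special interest by a term list: every TEAE or TESAE "of bleeding that emerged following randomization up to Study Day 91 for each subject will be identified by the terms listed in" SAP Appendix D. For each of four periods up to Study Day 91 and by treatment group, it then reports event totals and "the number of subjects with at least one bleeding TEAE, with more than one bleeding TEAE". The same is done for TESAEs, and heparin use is shown alongside. The section describes no medical review or other fallback for events outside the list. It does not say whether the list is matched to the investigator's term or to the MedDRA Preferred Term, or whether the match is exact or by text.

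The protocol's Appendix D (the pharmacovigilance guide) contains tables of adverse events for this product. The ELAD System (device) table includes "Catheter site haemorrhage". The long table just before the text on extracorporeal procedures includes "Vessel puncture site haematoma", "Gingival bleeding", epistaxis, haematuria and ecchymosis. In its list of laboratory changes, the same appendix refers to "other clinically overt sources of bleeding (e.g., hematuria, central line bleeding"). Its recording instructions use hematuria as the example of a clinical event that sites should enter when hemoglobin is affected.

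SAP Appendix D also lists terms such as "Premenstrual headache" and "Delayed menarche".

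**The concern.** The list decides who counts as a bleeding subject, so a gap or a stray entry passes straight into the tables. A subject whose only bleeding event in a period is haematuria or epistaxis would be counted as free of bleeding. A subject whose only matching event is a premenstrual complaint would be counted as having bled.

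Bleeding matters here. The protocol's Appendix D names an increased bleeding risk from anticoagulation among the expected risks of treatment, and its Appendix E provides for heparin in the ELAD circuit. The SAP 8.3.1.3 tables are the only planned place where bleeding subjects are pooled across terms and set beside heparin use.

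The general tables in SAP 8.3 do not replace them. They show each Preferred Term, but a subject is counted once per level and can appear in several term rows, so the number of subjects with any bleeding event cannot be recovered by adding rows.

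**Working it through.** The documents give no figure to reproduce on this point. The check compares two term lists.

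**1. Size of the SAP list.** SAP Appendix D has 86 lines. Five are UK/US spelling pairs of the same term, so 86 − 5 = 81 distinct terms.

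**2. Protocol bleeding terms.** The device table has 3: catheter site haemorrhage, haemorrhage and rectal haemorrhage. The long table has 13: application site bleeding, catheter site hematoma, catheter site hemorrhage, ecchymosis, epistaxis, gastrointestinal haemorrhage, gingival bleeding, haematemesis, haematuria, haemorrhage, injection site haemorrhage, melaena and vessel puncture site haematoma. Two appear in both tables, so 3 + 13 − 2 = 14. The heading and introduction of the long table are not in the text I could read, so 14 is a count of readable terms.

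**3. Protocol terms missing from the SAP list, by matching rule.** Spelling is harmonised throughout.

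| Rule | Missed, of 14 | Missed, of 13 (ecchymosis not counted as bleeding) |
|---|---|---|
| Literal exact match | 6 (42.9%) | – |
| Exact, application site bleeding accepted as application site haemorrhage | 5 (35.7%) | 4 (30.8%) |
| A listed term found as text inside the reported term, same synonym | 4 (28.6%) | 3 (23.1%) |
| As above, with bleeding read as haemorrhage everywhere | 3 (21.4%) | 2 (15.4%) |

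The five missed in the second row are haematuria, epistaxis, gingival bleeding, vessel puncture site haematoma and ecchymosis. Text matching recovers the puncture-site term through the listed entry haematoma. The bleeding/haemorrhage synonym also recovers gingival bleeding. Ecchymosis is borderline because skin haemorrhage and subcutaneous haemorrhage are listed. Haematuria and epistaxis are missed in every row.

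**4. Entries that are not bleeding.** The menstrual block has 22 entries, of which 8 denote bleeding and 22 − 8 = 14 do not. Setting aside three ambiguous ones (menstruation irregular, polymenorrhoea, retrograde menstruation) leaves 11. As shares of the list, 11/86 = 12.8% and 14/86 = 16.3%; of the distinct terms, 11/81 = 13.6% and 14/81 = 17.3%. Portal hypertensive gastropathy and portal hypertensive enteropathy name conditions that can bleed but do not themselves state that bleeding occurred.

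**5. Effect on the counts.** Omissions can only lower the number of bleeding subjects, and non-bleeding entries can only raise it. The net direction is not determined. The documents give no event rates for these terms. Safety-population arm sizes are not fixed either, because SAP 3.4 moves untreated ELAD subjects to Control. If an arm held 60 to 90 subjects (an assumption), one misclassified subject would move its incidence by 1/60 = 1.7 to 1/90 = 1.1 percentage points. How many such subjects there would be cannot be derived.

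**The case against.** The case for leaving the list alone has real substance.

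- **No rule is broken.** The protocol's Appendix D is a guide for attributing events to cells, device or procedure. It defines no bleeding group, and the SAP never promises to match it. This stands for most of the terms. It does not stand for haematuria, which the protocol itself describes as overt bleeding.
- **Coding may rescue some terms.** Events are coded to MedDRA 18.1, and the protocol table mixes coded and lay wording. Mucocutaneous haemorrhage, skin haemorrhage and haematoma are on the SAP list, so some of the omitted terms might be captured. A reader might take 5 of 14 as a firm loss. The documents do not support that, because the figure depends on an unstated matching rule, on the coding and on the readable text.
- **The data are not lost.** SAP 8 promises individual listings of all CRF data, and SAP 8.3 promises listings of all TESAEs, so anyone can regroup the events by subject. Low hemoglobin, blood products and circuit blood loss are also reported (SAP 8.5, 8.4 and 8.10.3). This stands and limits the harm, but it does not correct the tables in 8.3.1.3.
- **The menstrual entries are nearly inert.** Subjects are adults with severe hepatitis, and menarche terms can hardly arise. This stands. The two portal hypertensive entries are more plausible in this population.

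A reader might also infer that bleeding is undercounted mainly in the ELAD arm, because all five omissions come from one table that may concern the ELAD procedure. The heading cannot be verified and no rates by arm are given, so that inference fails. Nor can it be said that the survival-by-bleeding tables in SAP 7.3.7 are affected: that section does not cite Appendix D, and it concerns serious events only.

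**Conclusion.** The concern holds as a minor point. Followed as written, the plan leaves haematuria and epistaxis out of its pooled bleeding counts whichever of the tried matching rules is used. Three further protocol terms are left out on exact matching, one of them borderline. The plan would also admit 11 to 14 menstrual entries that are not bleeding and two portal hypertensive entries that need not be.

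The number of subjects with at least one, or more than one, bleeding TEAE or TESAE can therefore be too low or too high, by an unknown amount. These tables are descriptive, with no test or decision attached. Overall survival and the secondary endpoints do not depend on them.

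Confidence is high for the two terms that are always missed. The range from 2 of 13 to 6 of 14 rests on assumptions about matching, synonyms and whether ecchymosis is bleeding.

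**What to change.** Before the analysis is run:

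1. Add haematuria and epistaxis to SAP Appendix D. Also add gingival bleeding, vessel puncture site haematoma and ecchymosis, or the MedDRA 18.1 Preferred Terms to which they code.
2. Remove the menstrual and premenstrual entries that do not denote bleeding. Review whether the two portal hypertensive entries belong.
3. State in SAP 8.3.1.3 that matching is on the Preferred Term, or name the field and rule that will be used.
4. Say in SAP 7.3.7 whether its bleeding tables use the same list.

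Adding five terms and removing 11 to 14 takes the list from 86 lines to 86 + 5 − 11 = 80 or 86 + 5 − 14 = 77, before any decision on the portal hypertensive entries. On exact matching with the application-site synonym, coverage of the readable protocol bleeding terms rises from 9 of 14 to 14 of 14.

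The cost is a revised list and a rerun of the 8.3.1.3 bleeding tables, plus those in 7.3.7 if they use the list. Trial conduct does not change. Reported counts may rise or fall.

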8.4 CONCOMITANT MEDICATIONS AND BLOOD PRODUCTS

Concomitant medications and blood products are those administered at any time between Randomization and through Study Day 91. Concomitant medications and blood products will be summarized by treatment group. Additionally, the following medications and blood products will be summarized by treatment group and study period:

Medications of interest

- Steroids;
- Pentoxifylline;
- N-acetyl cysteine;

Additional medications of interest

- Antibiotics;
- Beta-blockers;
- Diuretics;
- Heparin;

- H₂ receptor antagonists;
- Proton pump inhibitors;
- Lactulose;
- Midodrine;
- Octreotide;
- Rifaximin;
- Vasopressors;

Blood products

- Albumin;

Selected medications will be evaluated based on proportions of subjects using each of the above classifications by treatment group and study period.

A summary of blood products administered during treatment and post-treatment periods will be presented by treatment group: descriptive statistics will be displayed by type of blood product, treatment group and the amount of blood product administered. In addition the number and proportion of subjects receiving certain accumulated amounts of blood products within defined treatment and post-treatment periods will be presented by treatment group.

Verbatim medication terms will be mapped to the Anatomical Therapeutic Chemical (ATC) classification system and Preferred Drug Names using the September 1st, 2015 version of the World Health Organization (WHO) dictionary. All concomitant medications and blood products will be summarized by ATC Level 3 and Preferred Name for proportions of subjects in each treatment group using each concomitant medication/blood product. Subjects will only be counted once within each level of summarization.

Concomitant medication and blood product use for medications of interest will be summarized in a similar manner based on proportions of subjects by treatment group, based on medications taken within treatment and post-treatment periods. The study periods used in analysis will be the same as described in the adverse event section ([Section 8.3](#)). The use of steroids, pentoxifylline and N-acetyl cysteine ([Singh et al. 2015](#)) will be of particular interest.

8.5 CHEMISTRY, HEMATOLOGY, COAGULATION, DISEASE-SPECIFIC EVALUATIONS

Data will be summarized by treatment group based on means by study visit, and mean (both absolute and %) changes from baseline by study visit. The baseline evaluation of a laboratory parameter is defined as the last evaluation of that parameter prior to randomization date/time. Additional summaries of changes relative to ELAD start date/time will be provided for subjects in the ELAD treatment group. For comparison purpose, changes relative to End of Study Day 2 will be summarized for the Control treatment group. Laboratory data will be prioritized over MELD/Maddrey data, if more than one measurement is recorded on the same study day.

For the following lab tests, proportion of subjects meeting the specified criteria will be presented by treatment group at each study visit:

- Bilirubin: <12 mg/dL vs. ≥12 mg/dL;
- Bilirubin: <16 mg/dL vs. ≥16 mg/dL;
- Hemoglobin: <7 g/dL;
- Platelet count: ≤20,000/mL;
- INR: >2.5 and >3.5;
- Calcium: ≤0.88 mmol/L;
- Glucose: >350 mg/dL or <50 mg/dL;
- Lactate: >4 mmol/L;
- Magnesium: <1.0 mEq/L;
- Phosphorus: <0.3 mmol/L;
- Potassium: >7.0 mEq/L or <2.0 mEq/L;
- Creatinine: Change <0.3 mg/dL vs. Change ≥0.3 mg/dL;
- Sodium: <130 mEq/L vs. ≥130 mEq/L;
- Sodium: <120 mEq/L.

No inferential statistical analyses will be performed for the summaries of laboratory data.

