Subjects with a platelet count $<20,000/\text{mm}^3$ without any clinical manifestations of bleeding during study treatment (ELAD and Control) will receive platelet transfusions based on the judgment of the clinical team. If the platelet count is $<20,000/\text{mm}^3$ and there are clinical manifestations of only localized contained bleeding, the subjects (ELAD and Control) must receive platelet transfusions. Subjects with a platelet count of $<20,000/\text{mm}^3$ and generalized bleeding are to be promptly assessed and, if on ELAD, considered for treatment discontinuation.

5.4.1.10 ***Standard of Care – ICU Discharge***

Subjects may be admitted to the ICU (or SDU where hospital standards allow and VTL approves) before or during the VTL-308 study. Therefore, the subjects' status should be continuously reviewed to identify subjects who no longer require ICU care. It is recommended that subjects be discharged from the ICU when their physiologic status has stabilized or when their physiological status has deteriorated and further interventions are not warranted. It is recommended that subjects experiencing alcohol withdrawal receive ICU care until their detoxification stage has stabilized (i.e., absence of seizures and delirium requiring intense monitoring). In addition, the subject experiencing alcohol withdrawal should be hemodynamically stable prior to discharge (i.e., not requiring intense monitoring for vasopressor administration or mechanical respiratory support). Continuous and frequent follow-up with the subject is recommended on the SDU or medical/surgical unit post-ICU discharge. For discharge from the ICU, a general guideline is that the subject is no longer in need of vasopressors, mechanical ventilation, or continuous extracorporeal renal treatment.

5.4.1.11 ***Standard of Care – Hepatic Hydrothorax***

Hepatic hydrothorax is defined as a large pleural effusion (usually unilateral and right-sided) that occurs in a subject with cirrhosis and ascites. The protein concentration in the pleural fluid is usually higher than in the ascitic fluid due to differences in the hydrostatic forces in the abdomen versus the chest. First-line therapy of hepatic hydrothorax consists of dietary sodium restriction and diuretics while TIPS is considered to be second-line treatment when it becomes refractory. Chest tube insertion is contraindicated in a subject with hepatic hydrothorax.

5.4.2 **Pre-Treatment**

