5.5.2 Safety Evaluations While on Extracorporeal Treatment (ELAD only)

The following study procedures will be completed during the first 24 hours of ELAD treatment (see [Table 3](#)):

- Vital signs (blood pressure, heart rate, respiration rate, and temperature) collected between hours 1-3, 6-10, and 14-18
- PT, PTT, INR, and platelet count collected between hours 6-10, and 14-18
- If anticoagulants are administered, they will be managed using the standard anticoagulation therapy protocol at the site (See [Section 5.5.2.1](#))

These 24-hour safety evaluations will all be repeated if the ELAD cartridges are replaced during treatment (See [Section 6.5](#)).

ELAD Specialists are responsible for all ELAD System management and monitoring. ELAD System performance will be monitored through pump speeds and system pressures (P_{BW} , P_{PUG} , P_{UF} , P_{EC} , P_F , P_{BR}). ELAD cartridge performance will be monitored by measuring oxygen, pH, glucose, and temperature.

The [ELAD System Operator's Manual](#) provides instructions for the management and monitoring of the ELAD System during treatment. The ELAD Specialists will document ELAD System performance in the ELAD System Monitoring Forms.

5.5.2.1 *Anticoagulation Therapy during ELAD Treatment*

Extracorporeal systems often require anticoagulation therapy. As an example, in subjects with a PTT of less than 50 seconds, extracorporeal circuits may clot more frequently than in subjects with a spontaneous PTT of more than 50 seconds if no anticoagulant is used. Please refer to anticoagulation guidance provided by the Sponsor in [Appendix E](#), and hospital standard of care for extracorporeal treatment.

Since anticoagulation therapy is associated with changes in coagulation parameters which may be more profound in patients with liver disease, the use of anticoagulants must be monitored according to the study site's internal procedures for continuous anticoagulation of extracorporeal circuits in subjects with increased bleeding risks.

The Investigator at each site is responsible for assessing the need of each subject for anticoagulation therapy prior to ELAD initiation and during ELAD treatment, and may consult with the study site's experts (e.g., intensive care staff, nephrology staff, or perfusionists) to apply

the study site's internal standards for anticoagulation of liver disease subjects on continuous extracorporeal circuits.

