8 SAFETY ANALYSIS

All safety analyses will use the Safety population, unless otherwise specified. All safety assessments will be summarized by treatment group. There may, in addition, be separate analyses of groupings of adverse events, laboratory values, or procedures of special interest.

Safety analyses will be summarized by treatment group (e.g., N, mean, median, SD and proportions, as appropriate). All analyses will be summarized by Study Day, as appropriate. Analyses will also be provided for the time periods during the treatment period and also for the time periods after the treatment ends. Factors related to post-treatment care and activities will be included in summaries of post-baseline distributions. All changes will be calculated relative to randomization date/time (as all subjects are on standard of care treatment as of the randomization date/time). Additional summaries of changes relative to ELAD start date/time will be provided for selected analyses. For comparative purpose, the Control group will be summarized by changes relative to End of Study Day 2, as this most closely mimics the time of initiation of ELAD treatment in those subjects randomized to ELAD. If Study Day 2 is missing for Control subjects, the last non-missing visit before Study Day 2 will be used for analysis.

Summaries of quantitative variables will include distributions by a clinically relevant discretization of each of the variables, along with computation of the mean, median, SD, minimum, and maximum. All data captured on the CRF will be presented in individual listings.

If a data point is collected more than once at the same visit, the last measurement will be used for analysis.

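### SAP 8.5 shows laboratory danger limits only visit by visit, using the last value at a visit, so no planned table gives the number of subjects who ever crossed a limit.

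*SAP*

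**What the plan says.** SAP 8.5 lists critical limits, among them "Hemoglobin: <7 g/dL", "Platelet count: ≤20,000/mL", INR above 2.5 and above 3.5, and high and low limits for glucose and potassium. For these the "proportion of subjects meeting the specified criteria will be presented by treatment group at each study visit". The section also plans means and mean changes by visit, and rules out inferential tests on laboratory data.

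Two rules decide which value enters. SAP 8 states for all safety analyses: "If a data point is collected more than once at the same visit, the last measurement will be used for analysis". SAP 8.5 adds: "Laboratory data will be prioritized over MELD/Maddrey data, if more than one measurement is recorded on the same study day". The second rule concerns bilirubin, creatinine and INR or PT, the laboratory inputs to those scores. Hemoglobin and platelets have no MELD or Maddrey source, so only the last-value rule applies to them.

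SAP 8 also promises in general terms: "Analyses will also be provided for the time periods during the treatment period and also for the time periods after the treatment ends". Neither section defines a worst-value, shift or any-time post-baseline table.

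**The concern.** A danger-limit table should answer two questions: how many subjects in each arm reached a dangerous value, and when. The planned tables answer only the second, and only for the value retained at each visit.

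This matters because Protocol Appendix D names anemia, coagulopathy and thrombocytopenia as the most common adverse events of extracorporeal procedures, and reports that hemoglobin tended to fall after ELAD was started in earlier studies. The by-arm count of subjects below a hemoglobin or platelet limit, or above an INR limit, is therefore a basic safety result. In SAP 8.3.1 the plan already counts subjects with at least one infection, fluid or bleeding event by period. The laboratory limits have no equivalent.

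**Working it through.** The plan states no figure for this point, so there is none to reproduce. The check has three steps.

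**1. What visit proportions reveal about subjects.** Let n be the arm size, V the number of visits and k the number beyond a limit at each visit, with all n subjects measured each time. The number ever beyond the limit lies between k (the same subjects every time) and min(n, k × V) (different subjects every time). If visits were independent, its expected value would be n × [1 − (1 − k/n)^V].

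Inputs:
- n = 75 per arm (SAP 1.3).
- V = 7 for the daily evaluations at End of Study Days 1 to 7 (Protocol Tables 2 and 3), or 12 with Days 14, 21, 28, 63 and 91 added.
- k is an assumption, because the documents give no crossing rates.

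| k at each visit | V | Lowest | Highest | If independent |
|---|---|---|---|---|
| 1 (1.3%) | 7 | 1 | 7 | 6.7 |
| 1 (1.3%) | 12 | 1 | 12 | 11.2 |
| 3 (4.0%) | 7 | 3 | 21 | 18.6 |
| 3 (4.0%) | 12 | 3 | 36 | 29.0 |
| 5 (6.7%) | 7 | 5 | 35 | 28.7 |
| 5 (6.7%) | 12 | 5 | 60 | 42.2 |

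For k = 3 and V = 7 the upper bound is 3 × 7 = 21 (28% of 75), and the independent case is 75 × (1 − 0.96^7) = 18.6. The same row of visit proportions fits every count from 3 to 21. This ambiguity exists even if no value is ever repeated within a visit.

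**2. What the last-value rule does.** Suppose two hemoglobin values are recorded at one visit, the first below 7 g/dL and the second above. The rule keeps the second, and the subject is counted as not meeting the criterion at that visit. The minimum and maximum promised in SAP 8 do not recover the first value: they describe the distribution of the analyzed values and are not defined as within-subject extremes.

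**3. Whether a simple any-value count would be fair.** For ELAD subjects only, Protocol 5.5.2 schedules in the first 24 hours of treatment "PT, PTT, INR, and platelet count collected between hours 6-10, and 14-18". Counting platelet and INR draws from Tables 2 and 3:
- Control: 12 scheduled visits + 1 matched safety check = about 13.
- ELAD: 12 + 1 pre-treatment safety check + 2 extra draws + 1 draw 24 hours after stopping = about 16.

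With an equal, independent crossing risk of 2% per draw (assumed), the share ever crossing is 1 − 0.98^13 = 23.1% in Control and 1 − 0.98^16 = 27.6% in ELAD, with no true difference. At 1% the figures are 12.2% and 14.9%; at 5% they are 48.7% and 56.0%. A per-subject count must therefore start from draws common to both arms.

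**The case against.** The strongest reply is that these events are captured elsewhere. Protocol 9.3 treats an abnormality that leads to therapeutic intervention as clinically significant, and hence reportable, in either arm. Appendix D gives numeric adverse-event triggers on ELAD that largely match the SAP 8.5 list. SAP 8.3 counts each subject once per Preferred Term, SAP 8.4 summarizes blood products by arm and period, and every CRF value is listed.

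Much of this stands: the values are not lost to the study report. It does not supply the count, for four reasons:
- Appendix D's numeric triggers apply only while on ELAD, and it says that laboratory changes in general should not be recorded as adverse events.
- Its hemoglobin trigger mixes a fall of more than 1.0 g/dL with a level below 7.0 g/dL. It gives no INR figure, although Protocol 9.3 mentions a raised INR as an example.
- An event may be recorded under a linked clinical diagnosis.
- Blood-product tables show use, and listings give no comparison by arm.

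A second objection is that the last-value rule may seldom matter. Chemistry and blood counts are scheduled once per Study Day (Protocol 5.5.1), and the extra ELAD draws are separate columns in Table 3. That also stands, although SAP 8.5 does not say how those columns map to a study visit.

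A reader might infer more: that transfusion erases low values before the last draw, and that the tables therefore understate harm most in ELAD subjects. Protocol 5.4.1.9 does say that, below 20,000/mm³ with localized bleeding, "the subjects (ELAD and Control) must receive platelet transfusions". But that rule is the same in both arms, and without bleeding the decision is left to clinical judgment. Nothing shows that values before and after transfusion are entered under one visit. ELAD subjects also have more scheduled platelet and INR draws, which raises detection.

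**Conclusion.** The point holds as a gap in the planned tables. They cannot show how many subjects ever crossed a danger limit, and they omit a same-visit extreme that is followed by a later value. The first part follows from the table definition and needs no assumed rate. Its illustrative size, 3 to 21 of 75 subjects, rests on an assumed 4% at each of 7 visits with complete data. The second part has no size that can be derived: neither its frequency nor any difference between arms can be told from the documents. A claim of biased reporting in favor of ELAD is not supported.

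The tables are descriptive and the overall survival analysis is untouched, so this is a cheap improvement to safety reporting rather than a flaw in the trial's main conclusion.

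**What to change.** Amend SAP 8.5 as follows.

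1. Keep the by-visit tables, but for the danger limits use the most extreme value at the visit in the direction of each limit. Treat high and low separately for potassium and glucose. The two-way splits for bilirubin and for sodium at 130 mEq/L can stay by visit as planned.
2. Add, by arm, the number and proportion of subjects with at least one post-baseline value beyond each limit: Randomization to Day 7, Days 8–14, Days 15–91 and overall. These follow the SAP 8.3 periods, joined in the first week because SAP 8.3 splits that week differently in the two arms.
3. Report the number of subjects with data in each period. Discharged subjects need not attend daily assessments (Protocol 5.5.1), so even the common schedule is not equally observed.
4. Present the count first from draws scheduled in both arms, then from all recorded values, with the extra ELAD platelet and INR draws shown separately.

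One unit needs reconciling before any platelet table is run. SAP 8.5 prints its platelet limit per mL, while Protocol 5.4.1.9 uses per mm³. Since 1 mL is 1,000 mm³, 20,000/mL equals 20/mm³, a thousandfold difference.

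The cost is SAP wording and one more descriptive table per parameter, from data already collected and without any hypothesis test. The downside for the sponsor is that ELAD safety figures may look less favorable.
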